8.2.2 Dose Adjustments

In General

Doses may be held or reduced for hematologic (see section 8.2.3) and other adverse events (see section 8.2.4). Dose adjustments are to be made according to the system showing the greatest degree of toxicity. Once dose is reduced due to adverse events, patients should not be re-challenged to a higher dose level.

Dose reductions or delays will be considered for the standard endocrine treatment and everolimus and may occur independently.

Due to the wide spectrum of feasible combinations of standard endocrine treatment and everolimus dose reductions and delays of standard endocrine treatment should follow general GCP criteria for the application of antineoplastic drugs (Repetto et al. 2003, NCCN-Guidelines) and should be made according to the SPC and/or investigator's brochure. The latest versions of the SPCs ("Fachinformation" according to German Drug Law) of the standard therapy will be provided on the DETECT IV website or by contact the DETECT Study Office in Ulm (Univeritäts-frauenklinik Ulm, Studienzentrale, [name], [name], [contact], [contact], Email: [contact]).

Subjects who require permanent discontinuation of one of the products due to unacceptable toxicities may switch to another treatment regime of the standard endocrine treatment if medically reasonable.

The antineoplastic treatment of a patient can be postponed for up to 4 weeks to allow resolution of toxicity. The investigator must consult the DETECT IV Study Office prior continuing therapy for any patient requiring a delay of study treatment of more than two weeks for any reason.

All patients who require permanent discontinuation of both everolimus and the endocrine agent in a given treatment combination will be withdrawn from the treatment intervention schedule (start of the 2-year follow-up period).

8.2.2.1 Permitted study drug dose adjustments and interruptions

For patients who are unable to tolerate the protocol-specified dosing scheme, dose adjustments and interruptions are permitted in order to keep the patient on the study drugs. The following guidelines should be followed.

These changes must be recorded on the Dosage Administration Record eCRF.

For patients with start dose of 5 mg daily and well tolerated treatment, increasing of everolimus dose to 10 mg daily is recommended according to the approved label.

Treatment with everolimus and standard endocrine therapy should continue as long as clinical benefit is observed or until unacceptable toxicity occurs. Management of severe and/or intolerable suspected adverse events may require temporary dose reduction and/or interruption.

For patients who do not tolerate the protocol-specified everolimus dosing schedule, dose adjustments are permitted in order to allow the patient to continue the study. The following guidelines need to be applied:

Dose adjustments are permitted for any adverse event suspected to be related to everolimus in those patients unable to tolerate their individual once daily oral dose. If administration of everolimus must be interrupted because of unacceptable toxicity, everolimus dosing will be interrupted or modified according to the guidelines in TABLE 14, TABLE 15 and TABLE 16 below.

In addition, if any surgery is planned, everolimus dosing should be interrupted one week prior to surgery and should be re-started as soon as possible after wound healing.

If everolimus dosing is interrupted due to toxicity, everolimus should not be resumed unless recovery to grade ≤ 1 is achieved in less than 4 weeks. Then everolimus could be reintroduced at the initial dose or a lower dose level depending on the toxicity type and grade(see TABLE14 , TABLE 15 and TABLE 16 below).

All study drug interruptions or dose modifications must be recorded on the Dosage Administration Record page of the eCRF.

Dose level	Dose and schedule
0 = starting dose	Last administered daily dose
-1 dose level	5 mg daily (if starting dose 10 mg daily)
	5 mg every other day (if starting dose 5 mg daily).

Minimal dose is 5 mg every other day.

Table 14: Everolimus dose reduction

If a patient has already decreased everolimus intake to 5 mg every other day, no further dose reduction is permitted. Patients requiring an additional everolimus dose reduction will be required to discontinue study treatment.

Patients who interrupt everolimus therapy for more than 4 weeks must be discontinued from the study.

TABLE 15 and TABLE 16 provide the procedure to be followed for everolimus dose modification in the event of toxicities suspected to be related to the everolimus treatment. Included are also instructions for re-initiation of everolimus dosing once sufficient recovery of toxicity is seen.

Toxicity	Actions
Metabolic events (e.g. Hyperglycemia, Hyperlipidemia and/or hypertriglyceridemia)	
Grade 1: No dose adjustment required. Initiate an appropriate medical therapy and monitor.
 
Grade 2: No dose adjustment required. Initiate an appropriate medical therapy and monitor.
 
Grade 3: Interrupt everolimus until recovery to grade ≤ 1. Reintroduce everolimus at the next lower dose level. . Initiate an appropriate medical therapy and monitor
 
Grade 4: Discontinue everolimus treatment

Stomatitis	
Grade 1: No dose adjustment required.
 
Grade 2: Interrupt everolimus until resolution to \leq grade 1. Restart at the same dose. If stomatitis recurs at grade 2, interrupt dose until recovery to grade ≤ 1. Restart at a lower dose.
 
Grade 3: Interrupt everolimus until recovery to grade ≤ 1. Reintroduce everolimus at the next lower dose level
 
Grade 4: Discontinue everolimus treatment

Pneumonitis	
Grade 1: No dose adjustment required. Initiate appropriate monitoring.
 
Grade 2: Consider interruption of therapy, rule out infection and consider treatment with corticosteroids until symptoms resolve to \leq grade 1. Restart at a lower dose. Discontinue treatment if failure to recover within 4 weeks.
 
Grade 3: Discontinue everolimus, rule out infection and consider treatment with corticosteroids until symptoms resolve to \leq grade 1. Consider restart at a lower dose level. Discontinue treatment if failure to recover within 4 weeks.
 
Grade 4: Discontinue everolimus treatment rule out infection and consider treatment with corticosteroids.

Other toxicities	
Grade 1: It toxicity is tolerable, no dose adjustment required.
 
Grade 2: It toxicity is tolerable, no dose adjustment required. It toxicity becomes intolerable, interrupt everolimus until resolution to \leq grade 1. Restart at the same dose. If toxicity recurs at grade 2, interrupt dose until recovery to grade \leq 1. Restart at a lower dose.
 
Grade 3: Interrupt everolimus until recovery to grade \leq1. Reintroduce everolimus at the next lower dose level
 
Grade 4 Discontinue everolimus treatment

Toxicity requiring interruption for >4 weeks	Permanently discontinue treatment.

No specific dose adjustments are recommended for Grade 1 toxicity. However, physicians should always manage patients according to their medical judgment based on the particular clinical circumstances.

Table 15: Everolimus dose modification guidelines for non-hematologic toxicities

Toxicity	Actions
Thrombocytopenia	
 $\geq 75000/\text{mm}^3$: No change
Platelet count	
 $50000/\text{mm}^3$ to $75000/\text{mm}^3$ Hold everolimus treatment until recovery to $\geq 75000/\text{mm}^3$ Reintroduce everolimus at the same dose level $< 50000/\text{mm}^3$ Hold everolimus treatment until recovery to $\geq 75000/\text{mm}^3$ Reintroduce everolimus at the next lower dose level, if available.
Absolute Neutrophil count (ANC)	
 $\geq 1000/\text{mm}^3$: No change $500/\text{mm}^3$ to $1000/\text{mm}^3$ Hold everolimus treatment until recovery to $\geq 1000/\text{mm}^3$ Reintroduce everolimus at the same dose level $< 500/\text{mm}^3$ Hold until recovery to $\geq 1000/\text{mm}^3$. Reintroduce everolimus (at the next lowest dose level, if available).
Febrile neutropenia	Hold further dosing until ANC $\geq 1250/\text{mm}^3$ and no fever. Then resume dosing at the next lower dose level, if available.
Toxicity requiring interruption for > 4 weeks	Permanently discontinue everolimus treatment

Physicians should always manage patients according to their medical judgment based on the particular clinical circumstances.

Table 16: Everolimus dose modification guidelines for hematologic toxicities

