Thrombocytopenia		
 Grade 1 ($\geq 75 \times 10^9$): No change
Platelet count		
 Grade 2 ($50 \times 10^9 - 75 \times 10^9$) Dose interruption until recovery to grade ≤ 1 Reintroduce ribociclib at the same dose level Grade 3 ($25 \times 10^9 - 50 \times 10^9$) Dose interruption until recovery to grade ≤ 1 Reintroduce ribociclib at the same dose level If toxicity recurs at grade 3: temporary dose interruption until recovery to grade ≤ 1 and reduce ribociclib to the next lowest dose level. Grade 4 ($<25 \times 10^9$) Dose interruption until recovery to grade ≤ 1 Reintroduce ribociclib at the next lower dose level. If toxicity recurs at grade 4: discontinue ribociclib.
Absolute Neutrophil count (ANC)	Neutrophil count	
 Grade 1 ($\geq 1,5 \times 10^9$): No change Grade 2 ($1,5 \times 10^9 - 10^9$): No change Grade 3 ($0,5 \times 10^9 - 1 \times 10^9$): Dose interruption until recovery to $\geq 1.0 \times 10^9/L$ Reintroduce ribociclib at the same dose level. If toxicity recurs at grade 3: temporary dose interruption until recovery to $\geq 1.0 \times 10^9/L$ If resolved in ≤ 7 days, then maintain dose level. If resolved in > 7 days, then reduce ribociclib dose to the next lower dose level. Grade 4 ($<0,5 \times 10^9$): Dose interruption until recovery to $\geq 1.0 \times 10^9/L$ Reintroduce ribociclib at the next lower dose level. If toxicity recurs at grade 4: temporary dose interruption until recovery to $\geq 1.0 \times 10^9/L$ And reduce ribociclib at the next lower dose level.
Febrile neutropenia		
 Grade 3 (ANC $< 1.0 \times 10^9/L$ with a single temperature of $> 38.3^\circ C$ or a sustained temperature of $\geq 38^\circ$ for more than one hour): Dose interruption until improvement of ANC $\geq 1.0 \times 10^9/L$ and no fever. Restart at the next lower dose level. If febrile neutropenia recurs, discontinue ribociclib. Grade 4 (Life-threatening consequences; urgent intervention indicated): Discontinue ribociclib.
Anemia (Hemoglobin)		
 Grade 1 ($\geq 10.0 \times LLN$ g/dl): No change Grade 2 ($\geq 8.0 - < 10 \times LLN$ g/dl): No change Grade 3 ($< 8.0 \times LLN$ g/dl):

Dose interruption until recovery to grade ≤ 2 .

Reintroduce ribociclib at the same dose.

• **Grade 4 (Life-threatening consequences; urgent intervention indicated):**

Discontinue ribociclib

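### Section 8.2.2.1 bars restarting everolimus above Grade 1, but the neutrophil and febrile neutropenia rows of Table 16 restart it at counts that the protocol grades higher

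*Protocol*

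**What the plan says.** Section 8.2.2.1 of the protocol governs interruption and restart of everolimus. Its general sentence is: "If everolimus dosing is interrupted due to toxicity, everolimus should not be resumed unless recovery to grade" 1 or lower is reached in under 4 weeks. The next sentence moves on to the dose: "Then everolimus could be reintroduced at the initial dose or a lower dose level depending on the toxicity type and grade", with a cross-reference to Tables 14, 15 and 16.

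Further on, the same section introduces Tables 15 and 16 as the procedure to follow and adds: "Included are also instructions for re-initiation of everolimus dosing once sufficient recovery of toxicity is seen". No grade is attached to that phrase.

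The haematological table is captioned "Table 16: Everolimus dose modification guidelines for hematologic toxicities". Its ANC rows are:
- At 1000/mm³ or above, no change.
- From 500 to 1000/mm³: "Hold everolimus treatment until recovery to $\geq 1000/\text{mm}^3$ Reintroduce everolimus at the same dose level".
- Below 500/mm³, hold until the count is at least 1000/mm³, then restart one level down where a lower level exists.
- After febrile neutropenia, hold until the count is at least 1250/mm³ and fever has gone, then restart one level down where a lower level exists.

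Numeric neutrophil grades are printed in one place only, Table 21 in section 8.3.2.1 (ribociclib). Grade 1 is 1.5 × 10⁹/L or more and Grade 2 is 1.0 to 1.5 × 10⁹/L. Appendix IV applies CTCAE version 4.03 to the whole trial.

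**The concern.** Within one section, a site is given two different conditions for restarting the same drug after the same event. The general sentence makes Grade 1 or lower the condition for any restart. Table 16 gives its own restart counts, and for neutrophils these lie outside Grade 1 on the protocol's printed bands. A patient whose count has recovered only into the gap may restart under the table but not under the sentence.

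At stake are the time off everolimus in such patients, uniform handling across up to 100 centres, and a restart rule that a monitor can check. It is a drafting contradiction in a safety-relevant instruction and does not touch the statistical design.

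**Working it through.** The protocol states no figure to reproduce here. The check puts the Table 16 restart counts on the printed grade bands and compares them with the general condition.

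**Inputs**
- General condition: Grade 1 or lower (section 8.2.2.1).
- Table 16 restart counts: ANC 1000/mm³ after neutropenia; ANC 1250/mm³ without fever after febrile neutropenia; platelets 75000/mm³.
- Printed bands (Table 21): neutrophil Grade 1 at 1.5 × 10⁹/L or more, Grade 2 from 1.0 to 1.5 × 10⁹/L; platelet Grade 1 at 75 × 10⁹/L or more.

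**Conversion:** count per mm³ ÷ 1000 = count in 10⁹/L.

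| Table 16 row | Restart count | In 10⁹/L | Printed grade | Meets Grade 1 or lower? |
|---|---|---|---|---|
| Neutropenia (both ANC hold rows) | 1000/mm³ | 1.0 | 2 | No |
| Febrile neutropenia (residual count) | 1250/mm³ | 1.25 | 2 | No |
| Platelets | 75000/mm³ | 75 | 1 | Yes |

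The printed Grade 2 and Grade 3 bands share the end point 1.0. On either side of it the count is not Grade 1.

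**Disputed range.** On the printed bands, Grade 1 or lower needs 1.5 × 1000 = 1500/mm³.
- After neutropenia: 1000 to below 1500/mm³, a band of 1500 − 1000 = 500 cells.
- After febrile neutropenia: 1250 to below 1500/mm³, a band of 1500 − 1250 = 250 cells. From 1000 to 1249/mm³ neither rule permits a restart.

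The mismatch is confined to these rows. The platelet row agrees with the general sentence, and where Table 15 names a recovery grade it is Grade 1 or lower.

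**How many patients.** Table 16 holds everolimus for a count below 1000/mm³, which is Grade 3–4 on the printed bands. The protocol's cited trials give Grade 3–4 neutropenia in 1 of 137 patients on everolimus plus letrozole (0.7%, Table 10) and in 1 of 54 on everolimus plus tamoxifen (2%, Table 8). Section 15.3 plans 90 everolimus patients.
- 90 × 0.007 = 0.6
- 90 × 0.02 = 1.8

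This is a rough count of patients who might be interrupted for neutropenia. How long a recovering count stays in the disputed range is not given in the protocol.

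**The case against.** The best defence is that the specific rule overrides the general one. Section 8.2.2.1 says dosing is to be modified according to Tables 14 to 16, describes Tables 15 and 16 as the procedure to follow, and says they contain restart instructions. Table 16 also requires no change at 1000/mm³ or above, so a count in the disputed range would not itself cause a hold. Table 21 uses the same restart count for ribociclib. Many sites would probably follow the table. This eases the conflict without removing it. The general sentence comes first, covers all toxicity, states no haematological exception, and cites Table 16 only for the step after Grade 1 or lower has been reached. No order of precedence is given.

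A second defence concerns febrile neutropenia. Table 21 treats it as a separate toxicity whose listed grades begin at 3, so at 1250/mm³ without fever the event has arguably resolved. That stands in part: only the residual neutrophil count is Grade 2, so this row is the weaker half of the point.

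That the bands are printed in the ribociclib table matters little, because CTCAE 4.03 applies to the whole trial and no other neutrophil scale is offered for everolimus.

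A reader might infer more than the documents support:
- **Permanent discontinuation under one rule, back on drug under the other.** The discontinuation rule is triggered by an interruption of more than 4 weeks, and a patient restarted under Table 16 is no longer interrupted. The paths diverge that far only if a site applies the general sentence strictly and the count stays between 1000 and 1499/mm³ until the 4 weeks have run out. The protocol gives no frequency for this.
- **A shift in the primary CTC sample.** Premature discontinuation of protocol treatment does trigger the Conclusion Visit with its blood sample (section 9.1), but that needs the same rare course. Section 8.2.2 also ties withdrawal from the treatment schedule to stopping both agents, while 8.2.2.1 and 13.1.1 are stricter. An effect on the clearance rate is not shown.
- **One or two patients harmed or misclassified.** The 0.6 to 1.8 concerns interruptions. A patient whose count soon passes 1500/mm³ would lose only days.

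**Conclusion.** The contradiction is real and narrow. The general recovery sentence and the neutrophil rows of Table 16 cannot both be followed at an ANC from 1000 to below 1500/mm³ after neutropenia. For the residual count after febrile neutropenia, the same holds from 1250 to below 1500/mm³. The conclusion rests on the bands printed in Table 21 and on reading the general sentence as written, without an unstated haematological exception.

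Its size is small. The estimate of about 0.6 to 1.8 of 90 patients with Grade 3–4 neutropenia assumes that the rates in the cited trials carry over. Each rate comes from one event, and the letrozole trial was in neoadjuvant early breast cancer. No material effect on the primary endpoint is shown. This is a minor point, worth correcting because it concerns a drug-restart instruction.

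**What to change.** The sponsor should reconcile the general recovery sentence in section 8.2.2.1 with the ANC and febrile neutropenia rows of Table 16, and state in the text which of them governs restart after haematological toxicity. Which threshold is clinically right is for the sponsor to decide, and none is proposed here.

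The cost is one sentence in the next amendment. Sample size, endpoints and analyses are unchanged.

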8.2.3 Known undesirable effects of the study drugs

Adverse events most frequently observed with everolimus are rash, stomatitis / oral mucositis, non-infectious pneumonitis, fatigue, headache, anorexia, nausea, vomiting, diarrhea, and infections. Overall, the most frequently observed laboratory abnormalities include neutropenia, thrombocytopenia, hypercholesterolemia, and/or hypertriglyceridemia. The majority of these AEs have been of mild to moderate severity (NCI CTC grade 1-2).

Recommendations for dose adjustments, should any of these treatment-related adverse events occur, are given in TABLE 14, TABLE 15 and TABLE 16.

8.2.3.1 Management of specific toxicities

Management of stomatitis/oral mucositis/mouth ulcers

Stomatitis/oral mucositis/mouth ulcers due to everolimus should be treated using local supportive care. Please note

that investigators in earlier trials have described the oral toxicities associated with everolimus as mouth ulcers, rather than mucositis or stomatitis. If examination reveals mouth ulcers rather than a more general inflammation of the mouth, please classify the adverse event as such. Please, follow the paradigm below for treatment of stomatitis/oral mucositis/mouth ulcers:

- For mild toxicity (grade 1), use conservative measures such as non-alcoholic mouth wash or salt water (0.9%) mouth wash several times a day until resolution.
- For more severe toxicity (grade 2 in which case patients have pain but are able to maintain adequate oral alimentation, or grade 3 in which case patients cannot maintain adequate oral alimentation), the suggested treatments are topical analgesic mouth treatments (i.e., local anesthetics such as benzocaine, butyl aminobenzoate, tetracaine hydrochloride, menthol, or phenol) with or without topical corticosteroids, such as triamcinolone oral paste 0.1% (Kenacort® A Orabase®).
- Agents containing hydrogen peroxide, iodine and thyme derivatives may tend to worsen mouth ulcers. It is preferable to avoid these agents.
- Antifungal agents must be avoided unless a fungal infection is diagnosed. In particular, systemic imidazole antifungal agents (Ketoconazole, Fluconazole, Itraconazole, etc.) should be avoided in all patients due to their strong inhibition of everolimus metabolism, therefore leading to higher everolimus exposures. Therefore, topical antifungal agents are preferred if an infection is diagnosed. Similarly, antiviral agents such as acyclovir should be avoided unless a viral infection is diagnosed.

Stomatitis/oral mucositis should be appropriately graded using the functional grading given on the NCI-CTC for Adverse Events, version 4.03.

Management of infections

Everolimus is an immunosuppressant. Patients taking everolimus are therefore at an increased risk of infection. In oncology patients, some infections have been severe and rarely have had a fatal outcome. Physicians should be aware of the increased risk of infection, and should warn patients and their caregivers to be vigilant for signs and symptoms of infection, and to seek medical attention immediately should such signs or symptoms occur. Should an infection occur, anti-infectives should be prescribed as clinically appropriate, and in the case of clinically significant infection, consideration should be given to withholding study medication until resolution of the infection.

Management of hyperlipidemia and hyperglycemia

Treatment of hyperlipidemia should take into account the pre-treatment status and dietary habits. Blood tests to monitor hyperlipidemia must be taken in the fasting state. Grade 2 or higher hypercholesterolemia (>300 mg/dL or 7.75 mmol/L) or Grade 2 or higher hypertriglyceridemia (>2.5 x ULN) should be treated with a statin (HMG-CoA reductase inhibitor), fibrate, or appropriate lipid-lowering medication in addition to diet. Patients should be monitored clinically and through serum biochemistry as required in the product label/data sheets for HMG-CoA reductase inhibitors.

Note: Concomitant therapy with fibrates and HMG-CoA reductase inhibitors are associated with an increased risk of a rare but serious skeletal muscle toxicity manifested by rhabdomyolysis, markedly elevated creatine kinase (CPK) levels and myoglobinuria, acute renal failure and sometimes death. The risk versus benefit ratio should be determined for individual patients based on their risk of cardiovascular complications of hyperlipidemia.

Hyperglycemia has been observed in patients receiving everolimus therapy. Monitoring of fasting serum glucose is recommended prior to the start of everolimus therapy and periodically thereafter. Optimal glycemic control should be achieved before starting trial therapy.

Management of diarrhea

Appearance of diarrhea attributed to everolimus toxicity may be treated with Loperamide. Other medications for diarrhea may be used as needed.

Management of non-infectious pneumonitis

Clinically significant pneumonitis is typically accompanied by non-specific symptoms including dyspnea, non-productive cough, fatigue and fever.

Worst Grade	Recommended Investigations	Management of Pneumonitis	Everolimus Dose Adjustment
Grade 1	CT scans with lung windows. Repeat chest x-ray/CT scan every 12 weeks until return to baseline.	No therapy required	Administer 100% of everolimus dose.
Grade 2	CT scan with lung windows. Repeat CT scan at least every 12 weeks until return to within normal limits. Consider bronchoscopy with biopsy and /or BAL.	Symptomatic only. Consider corticosteroids if cough is troublesome.	Consider interruption of everolimus until recovery to \leq Grade 1. Study. Restart treatment at a reduced dose. Patients will discontinue everolimus if they fail to recover to $<$ Grade 1 within 4 weeks
Grade 3	CT scan with lung windows. Repeat at least every 8 weeks until return to within normal limits. Bronchoscopy with biopsy and/or BAL is recommended.	Prescribe corticosteroids if infective origin ruled out. Taper as medically indicated.	Hold everolimus treatment until recovery to \leq Grade 1. May restart treatment within 4 weeks at a reduced dose (by one level**) if evidence of clinical benefit.
Grade 4	CT scan with lung windows and required pulmonary function testing including spirometry, DL _{CO} , and room air O ₂ saturation at rest. Repeat at least every 8 weeks until return to within normal limits. Bronchoscopy with biopsy and/or BAL is recommended if possible.	Prescribe corticosteroids if infective origin ruled out. Taper as medically indicated.	Discontinue everolimus treatment.

Table 17: Management of non-infectious pneumonitis

Both asymptomatic radiological changes (Grade 1) and symptomatic non-infectious pneumonitis (Grade 2 = not interfering with activities of daily living and Grade 3 = interfering with activities of daily living and oxygen indicated) have been noted in patients receiving everolimus therapy. Non-infectious pneumonitis has been associated with everolimus and other mTOR inhibitors (Atkins et al. 2004). If non-infectious pneumonitis develops, a consultation with a pulmonologist should be considered. If the patient develops Grade 3 pneumonitis, treatment with everolimus must be interrupted and the patient treated as medically indicated (short course corticosteroids, oxygen, etc.). Management of non-infectious pneumonitis suspected to be associated with everolimus (TABLE 17) and dose modification instructions are provided in TABLE 14 , TABLE 15 and TABLE 16.

